8.3 Potential Benefits

According to previous studies into the role of LP in reward processing and substance use disorders, and based on the impact of LP DBS in modulating compulsive behaviors, targeting of the LP with DBS is expected to provide benefit in preventing relapse to alcohol, reduce the risk of ALD-related mortality, and improve quality of life. Reductions in alcohol consumption are associated with reduced prevalence of psychiatric comorbidities (e.g., anxiety, depression), lower psychosocial stress levels, and improved social functioning and self-confidence [156]. Overall, patients are expected to benefit from lower mortality risk and better overall functioning, independence, and quality of life.

9 Protection Against Risks

9.1 Management of device related adverse effects

Steps to prevent and manage risks related to DBS surgery, stimulation, and optimization:

DBS surgery: All participants will be required to sign a durable power of attorney because of the possibility that they may become unable to make decisions about their care and research participation during the course of participation. The surgery protocol, operation room, and DBS hardware are consistent with standards of clinical care. Post-op head CT will be obtained immediately after the surgery and prior to moving the participant to the recovery room. In the recovery room, blood pressure and mental status will be monitored by nursing every 30 min and a neurologist will perform serial mental status and neurological exams until the participant leaves the recovery room. Participants will be followed closely by the study team after the surgery through in-person post-op visits and regular phone calls and emails to monitor their recovery and screen for potential complications. If a non-emergent complication were to arise, the participants would be seen by the study physicians. If the complication were an emergency, they would be instructed to call 911 and report to the closest emergency department. In addition, and to minimize risk of bleeding related to the device surgery, we will check blood tests (platelet count, function, PT, aPTT, thrombin time, reptilase time, fibrinogen activity/antigen, thromboelastogram) that evaluate bleeding risk prior and then on surgery day.

DBS titration/optimization/stimulation: After DBS optimization and turning the DBS system ON, we will check in with all patients by phone 3-7 times per week to screen for adverse effects until their first follow-up visit 2 weeks later. Each participant will receive a copy of the Medtronic Patient Therapy Guide prior to DBS surgery and individual teaching regarding the contents of the Guide. Participants will also receive a smaller pocket-size Quick Guide reference and a patient controller for safety, which allows them to turn DBS system off in case of severe side effects from stimulation. In case of moderate side effects due to the stimulation, participants will be evaluated and the DBS re-programmed; stimulation-related side effects are usually reversible by adjusting the stimulation parameters and re-programming the DBS system. The system can be turned off if symptoms are more severe or unattenuated by re-programming.

Similarly, if participants experience **increased alcohol use** compared to baseline as indicated in their monthly AUD assessment, we will 1) adjust DBS stimulation settings, and 2) the participant will be evaluated by the study psychiatrist to identify the clinical risk from increased drinking and potential clinical interventions to mitigate this risk. If alcohol use continues to be elevated compared to baseline during two following evaluations, we will turn the DBS off and consult with the DSMB.

Risks of electromagnetic interference: The Percept neurostimulator is designed to protect against most electromagnetic interference. However, strong electromagnetic fields can still interfere with the system, even when the DBS system is turned off (interference can affect the DBS leads). In such cases, participants will be instructed on the potential risks and possible sources of electromagnetic interference, and what to do when interference is suspected: 1) move away from the source of the interference, 2) turn off the suspected source of interference, 3) use the control magnet to turn their DBS unit off, and 4) call the study team.

DBS explantation: similar to DBS implantation.

DBS risk after study completion: if participants with beneficial DBS choose to keep DBS implanted, they will be followed up in the Neurology and Psychiatry clinics of study investigators in standard of care visits. These evaluations will screen for delayed adverse effects caused by DBS.

9.2 Management of research related risks

- **Protecting confidentiality:** Confidentiality of patient information will always be maintained. All members of the study team will have the required human subjects and confidentiality training, which includes information about maintaining data integrity and security. Confidentiality will be guarded using established procedures such as storing data in locked cabinets within locked offices or locked data rooms. Case report forms are coded by study identification numbers rather than any personal identifying information to avoid revealing the identity of subjects. Data analyses will be performed using the research codes as identifiers. All data will be encrypted prior to any electronic transfer. Electronic records will be kept in computer files that are password-protected and housed on the UPMC network behind the UPMC firewall. The key linking names and study identification numbers will be kept at the study site but separately from the data sets with limited access by study personnel. Only study personnel will have access to the data sets on protected servers.

- **Incidental findings:** In the case of incidental findings (e.g., blood tests, imaging), these will be discussed with the participant by a study physician who will refer them to their PCP or to a specialist for follow up, depending on the nature of the incidental finding.
- **Electrocardiogram:** This will be done by experienced staff to minimize skin irritation.
- **Blood tests:** These will be done by experienced nursing staff to minimize complications.
- **Liver ultrasound:** This will be done by experienced staff to minimize discomfort.
- **Brain MRI with contrast:** Subjects will be asked to complete an MR-screening form for each MR-scan. Participants will be screened for the presence of any contraindications to MRI before having any scan, and if they have any, they will be excluded from the study (see exclusion criteria) and will not receive an MR-scan. If subjects have a question about any metal objects being present in their body, they will inform the staff and an x-ray image will be obtained to rule out metal objects. In addition, all magnetic objects (watches, coins, jewelry, credit cards, etc.) must be removed before entering the MRI-scan room. All women of childbearing potential will have a pregnancy test performed no more than 24 hours before the MRI scan. The scan will not be done if the pregnancy test is positive. Participants will be fitted with hearing protection and subjects will notify staff of any hearing or ear problems. If a participant is claustrophobic, we will attempt to do the MRI scan in an open scanner or give them 1 mg oral lorazepam to help with the anxiety. If that remains an issue, the participant will be excluded from the study. We will test liver and kidney functions within 1 week of the MRI scan. Subjects will not receive gadolinium contrast if their kidney function is not normal.

For the post-implantation MRI, we will follow the FDA-approved MRI recommendations detailed in Medtronic's labeling, found in the document titled "MRI guidelines for the Medtronic DBS systems" for model B35200.

- **Radiation exposure:** (PET scans, Head CT scans): The maximum whole body cumulative exposure from PET and CT scans is 1.056 rem in a 12-month period. The maximum total radiation dose-exposure-equivalent to the urinary bladder is 7.2 rem in a 12-month period. These are less than the single study annual limit for both whole-body (5 rem) and dose-limiting critical organ (15 rem) under proposed guidelines for RDRC studies. Please see section above regarding radiation exposure during this study.
Female participants of childbearing age must use an effective method of contraception (birth control) from the time of enrollment until the end of the study in order to avoid exposure of fetuses to the radiation required by procedures this study. A pregnancy test will be obtained within 24 hours of every PET/CT scan.
- **Fasting before PET scans or liver US:** Subjects are allowed to drink water and take their meds. If they report symptoms of hypoglycemia like lightheadedness, we will check their blood glucose (part of the PET protocol) and if hypoglycemic, they may break their fasting. Subjects will be allowed to eat and drink after the PET scan or liver US are done.
- **Contraception:** If a participant experiences significant side effects from the contraception method she chose, we will recommend she consults with her PCP or OB/Gyn doctor to switch her contraception method.
- **Questionnaires:** If any of the questions trigger significant emotions that put the participant at risk, the participant will be evaluated and treated according to clinical care guidelines by the study team, including psycho-emotional support, medications, or admission, as deemed necessary by the treating study psychiatrist.
- **Neuropsychological evaluation:** Participants will be given breaks as needed during the evaluation.

- Alcohol withdrawal: participants will be educated about the risks of alcohol withdrawal and if they experience any withdrawal symptoms, they will be advised to come in for evaluation by study physicians or referred to a detox center.
- Cognitive and behavioral tasks: Experienced Psychiatry Department study staff will be present at all times during cue exposure and will provide support and conduct relaxation techniques until craving returns to pre-exposure levels. **Electroencephalogram:** This will be done by experienced staff to minimize discomfort.
- **Financial risks during study:** all the costs of the study procedures and interventions will be covered by the study funding agency. To minimize the financial burden related to lost productivity, travel, parking, and food costs, participants will be reimbursed for their time, parking and food costs for every study visit. They will receive \$200 for every full day evaluation visit, \$100 for every follow-up visit, and \$200/day for every admission day to the hospital (during implantation or explantation surgery). They will also receive up to \$70 for cognitive tasks (CGT and BART), \$20/day for parking and \$30/day for food. To reduce travel burden, we will also offer enrolled participants access to a ride service (e.g., Uber, Access). Participants will receive \$750 bonus upon completion of the study.
- **Financial risks after study completion:** to minimize the financial risks after study completion, subjects that did not benefit clinically from the DBS will have the DBS system explanted. Subjects who benefited significantly from DBS will be given the option to have the DBS explanted (no financial risk beyond study duration). If they choose to keep the DBS implanted, we will work with their insurance company or the Center for Medicare and Medicaid services (CMS) to cover the costs of follow up visits and battery replacement if needed given the clinical benefit they experienced from DBS. The clinical benefit translates into reduced mortality, reduced disability, improved overall functioning, and improved quality of life. We will also explain to the participants that even if they were to pay for the follow-up visits and battery replacement themselves, in a cost-benefit analysis, the financial risk from the incurred costs is minimal compared to the tremendous benefit these subjects receive from the treatment of their severe AUD with DBS (a priori, the DBS has to be efficacious in subjects who keep it implanted). We will also work with the participant's insurance company or CMS if after opting to keep the DBS system in, they decide to have it explanted after the study has ended, especially if it was deemed to be no longer necessary and the participant has achieved sustained remission.

10 Adverse Device Effects

The proposed clinical trial will use the following definitions:

Adverse effect. Any untoward medical occurrence in a clinical study of an investigational device; regardless of the causal relationship of the problem with the device or, if applicable, other study treatment or diagnostic product(s).

Associated with the investigational device or, if applicable, other study treatment or diagnostic product(s). There is a reasonable possibility that the adverse effect may have been caused by the investigational device or, if applicable, the other study treatment or diagnostic product(s).

Disability. A substantial disruption of a person's ability to conduct normal life functions.

Life-threatening adverse effect. Any adverse effect that places the subject, in the view of the investigator-sponsor, at immediate risk of death from the effect as it occurred (i.e., does not include an adverse effect that, had it actually occurred in a more severe form, might have caused death).

Serious adverse effect. Any adverse effect that results in any of the following outcomes: death, a life-threatening adverse effect, inpatient hospitalization or prolongation of existing hospitalization, a persistent or significant disability/incapacity, or a congenital anomaly/birth defect.

Unexpected adverse effect. Any adverse effect, the frequency, specificity or severity of which is not consistent with the risk information described in the clinical study protocol(s).

Unanticipated adverse device effect. Any serious adverse effect on health or safety or any life-threatening problem or death caused by, or associated with, a device, if that effect, problem, or death was not previously identified in nature, severity, or degree of incidence in the investigational plan or IDE application (including a supplementary plan or application), or any other unanticipated serious problem associated with a device that relates to the rights, safety, or welfare of subjects.

Adverse effects will be assessed on each participant at regular intervals throughout participation. When an adverse effect is discovered, the event will be assessed for severity, relatedness and expectedness. All adverse events will be documented in the research records and followed until resolved or back to baseline state.

10.1 Assessment of Severity

The study team will promptly review documented adverse effects and abnormal test findings. For all adverse effects, sufficient information will be pursued and/or obtained so as to permit 1) an adequate determination of the outcome of the effect, and 2) an assessment of the causal relationship between the adverse effect and any of the study interventions or procedures.

Adverse effects or abnormal test findings felt to be associated with the study interventions or procedures will be followed until the effect (or its sequelae) or the abnormal test finding resolves or stabilizes at a level acceptable to the study team.

Abnormal test findings: An abnormal test finding will be classified as an adverse effect if one or more of the following criteria are met:

- The test finding is accompanied by clinical symptoms.
- The test finding necessitates additional diagnostic evaluation(s) or medical/surgical intervention,
- The test finding leads to a change in study dosing or exposure or discontinuation of subject participation in the clinical study.
- The test finding is considered an adverse effect by the investigator-sponsor.

10.2 Relatedness

The proposed clinical trial will use the following definitions:

- Definitely Related – There is clear evidence to suggest a causal relationship, and other possible contributing factors can be ruled out. The adverse effect, including an abnormal laboratory test result, occurs in a plausible time relationship to study intervention administration and cannot be explained by concurrent disease or other drugs or chemicals.
- Probably Related – There is evidence to suggest a causal relationship, and the influence of other factors is unlikely. The adverse effect, including an abnormal laboratory test result, occurs within a reasonable time after the study intervention, is unlikely to be attributed to concurrent disease or other drugs or chemicals.
- Possibly Related – There is some evidence to suggest a causal relationship. However, other factors may have contributed to the adverse effect. Although an adverse effect may rate only as “possibly related” soon after discovery, it can be flagged as requiring more information and later be upgraded to “probably related” or “definitely related”, as appropriate.
- Unlikely to be related – An adverse effect, including an abnormal laboratory test result, whose temporal relationship to study intervention administration makes a causal relationship improbable and in which other drugs or chemicals or underlying disease provides plausible explanations.
- Not Related – The AE is completely independent of study intervention administration, and/or evidence exists that the adverse effect is definitely related to another etiology. There must be an alternative, definitive etiology documented by the clinician.

If the study team’s final determination of causality is “unknown and of questionable relationship to the study interventions”, the adverse effect will be classified as associated with the use of the study interventions for reporting purposes. If the study team’s final determination of causality is “unknown but not related to study interventions”, this determination and the rationale for the determination will be documented in the respective subject’s case history.

10.3 Expectedness

The Multiple Principal Investigators will be responsible for determining whether an adverse event is expected or unexpected based on the known risks of DBS and similar interventions. An adverse event

will be considered unexpected if the nature, severity, or frequency of the event is not consistent with the risk information previously described.

10.4 Adverse events reporting

A summary of the unanticipated adverse device effects that occurred during the previous year will be included in the FDA annual progress report as well as in the annual IRB continuing review and to the DSMB.

10.4.1 FDA Reporting

The investigator-sponsor will submit a completed FDA Form 3500A to the FDA's Center for Devices and Radiological Health for any observed or volunteered adverse effect that is determined to be an unanticipated adverse device effect. A copy of this completed form will be provided to all participating sub-investigators.

The completed FDA Form 3500A will be submitted to the FDA as soon as possible and, in no event, later than 10 working days after the investigator-sponsor first receives notice of the adverse effect.

If the results of the sponsor-investigator's follow-up evaluation show that an adverse effect that was initially determined to not constitute an unanticipated adverse device effect does, in fact, meet the requirements for reporting; the investigator-sponsor will submit a completed FDA Form 3500A as soon as possible, but in no event later than 10 working days, after the determination was made.

For each submitted FDA Form 3500A, the sponsor-investigator will identify all previously submitted reports that addressed a similar adverse effect experience and will provide an analysis of the significance of newly reported adverse effect in light of the previous, similar report(s).

Subsequent to the initial submission of a completed FDA Form 3500A, the investigator-sponsor will submit additional information concerning the reported adverse effect as requested by the FDA.

10.4.2 IRB Reporting

In accordance with applicable policies of the University of Pittsburgh Institutional Review Board (IRB), the investigator-sponsor will report, to the IRB, any observed or volunteered adverse effect that is determined to meet all of the following criteria: 1) associated with any of the study interventions; 2) a serious adverse effect; and 3) an unexpected adverse effect. Adverse event reports will be submitted to the IRB in accordance with the respective IRB procedures.

Applicable adverse effects will be reported to the IRB as soon as possible and, in no event, later than 10 calendar days following the investigator-sponsor's receipt of the respective information. Adverse effects which are 1) associated with any of the study interventions; 2) fatal or life-threatening; and 3) unexpected will be reported to the IRB within 24 hours of the investigator-sponsor's receipt of the respective information.

Follow-up information to reported adverse effects will be submitted to the IRB as soon as the relevant information is available. If the results of the sponsor-investigator's follow-up investigation show that an adverse effect that was initially determined to not require reporting to the IRB does, in fact, meet the

requirements for reporting; the investigator-sponsor will report the adverse effect to the IRB as soon as possible, but in no event later than 10 calendar days, after the determination was made. Any major disputes between the study investigators and a participant, or between research investigators, will be promptly reported to the IRB.

11 Withdrawal of Subjects and Stopping Rules

11.1 Adverse Events Requiring Discontinuation

Safety Monitoring Boundaries: Every adverse effect (AE) will be evaluated for severity, expectedness and relatedness and reported to the DSMB. The study will be discontinued (pending DSMB review) if any of the following occurs:

- A higher rate or severity of AE that are definitely, probably, or possibly related to LP DBS compared to standard of care DBS, as assessed by the DSMB.
- Any death, suicide attempt, disability, or other serious AE that is definitely, probably, or possibly related to LP DBS.
- Increased alcohol use in one participant compared to baseline ($>2x$ baseline DDD or $<2x$ PDA) that did not improve with adjusting DBS settings, as identified by AUD assessments in 3 consecutive follow-up visits.

If the study team proposes a well-justified and implementable plan on mitigation of such events, then the study could resume if the DSMB, IRB, and FDA agree.

All other serious adverse events and unexpected events will be reported to and discussed with the DSMB prior to continuing protocol enrollment. The occurrence of a serious adverse event will be grounds for unblinding the data for that participant.

11.2 Other Criteria Requiring Discontinuation

If participants turn their DBS system off more than 50% of the time, which is unprompted by adverse effects, and if they continue to turn it off after discussion with the team, they will be withdrawn from the study and their DBS explanted.

Beginning chemotherapy or other investigational medications after enrollment will result in the subject's discontinuation from the study.

Beginning anticoagulation after enrollment and before DBS implantation will result in the subject's discontinuation from the study.

If a patient no longer wishes to continue their participation in the study, they may elect to withdrawal from the study. Normal recruitment procedures will resume to replace any participant withdrawals (see recruitment description in section 5.4).

11.3 Clinical Trial Stopping Rules

This study may be temporarily suspended or prematurely terminated if there is sufficient reasonable cause (see **section 11.1: Safety Monitoring Boundaries**). Written notification, documenting the reason for study suspension or termination, will be provided by the study team to study participants, DSMB, IRB, NIAAA, and FDA. Study participants will be contacted, as applicable, and be informed of changes to study visit schedule.

Circumstances that may warrant termination or suspension include, but are not limited to:

- Determination of unexpected, significant, or unacceptable risk to participants:
 - A higher rate or severity of AE that are definitely, probably, or possibly related to LP DBS compared to standard of care DBS, as assessed by the DSMB.
 - Any death, suicide attempt, disability, or other serious AE that is definitely, probably, or possibly related to LP DBS.
 - Increased alcohol use in one participant compared to baseline (>2x baseline DDD or <2x PDA) that did not improve with adjusting DBS settings, as identified by AUD assessments in 3 consecutive follow-up visits.
- Demonstration of efficacy that would warrant stopping
- Insufficient compliance to protocol requirements
- Data that are not sufficiently complete and/or evaluable
- Determination that the primary endpoint has been met
- Determination of futility

Study may resume once concerns about safety, protocol compliance, and data quality are addressed, and satisfy the DSMB, IRB and/or FDA.

12 Statistical Analysis

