3.3 Endpoints

Primary endpoints: safety, tolerability, and feasibility

Safety and tolerability will be evaluated based on adverse events associated with DBS implantation and stimulation (e.g., infection, bleeding, cognitive or behavioral side effects). We will screen for adverse events using 4 approaches: **1)** patient self-report, **2)** clinical evaluations (medical, neurologic, and psychiatric), **3)** questionnaires to screen for depression, anxiety, apathy, and mania, and **4)** neuropsychological evaluation to screen for any LP DBS effects on the various cognitive domains. These will be compared to DBS side effects observed in FDA approved indications like PD.

Feasibility will be evaluated based on **1)** our ability to recruit all 3 patients within the indicated timeframes, **2)** our ability to conduct the necessary evaluations in baseline and follow-up assessments (e.g., alcohol use, PET imaging, cognitive and behavioral tasks) and **3)** patients' adherence to the study protocol and participation in follow-up visits and assessments.

These outcomes will be monitored throughout the entirety of the study (including recruitment, screening procedure, clinical evaluations, DBS implantation, DBS titration, and all other study-related procedures).

Secondary endpoints: alcohol use, overall functioning, and target engagement

Alcohol use: this will be measured by calculating percent days abstinent (PDA), drinks per drinking day (DDD), blood phosphatidylethanol (PEth) and blood gamma-glutamyl transferase (GGT); PDA and DDD are obtained from TimeLine Followback (TLFB) assessment of alcohol use over the past 180 days for baseline evaluation, and over the past 30 days for follow-up evaluations after DBS implantation. PEth and GGT are blood tests obtained at baseline and every month during follow up visits.

Overall functioning and disability: this will be measured using World Health Organization Disability Assessment Schedule 2.0 (WHODAS 2.0) at baseline and during monthly evaluations after DBS implantation.

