12.4 Analysis of Secondary Endpoints

The secondary outcomes are:

- 1) *Alcohol use* measured as PDA, DDD, PEth, GGT at baseline and monthly after DBS implantation.
- 2) *Overall functioning* and disability measured with the WHODAS 2.0 scale at baseline and monthly after DBS implantation.
- 3) *Target engagement* measured with FDG-PET scans at 3 time points: pre-DBS baseline, post-DBS-OFF, and post-DBS-ON at 6 months.

The secondary outcome *PDA* as a measure of *alcohol use* is a proportion, collected at baseline and during follow-up and assessment visits (1 baseline and 12 monthly post-DBS measurements).

The other measures of alcohol use (*DDD, PEth, GGT*) and the overall functioning score *WHODAS 2.0* are continuous variables collected at baseline and during follow-up and assessment visits (1 baseline and 12 monthly post-DBS measurements).

Alcohol use and overall functioning

H3: LP DBS reduces alcohol use and improves overall functioning in subjects with severe AUD compared to baseline. Specifically, LP DBS increases PDA, and decreases DDD, PEth, GGT and WHODAS 2.0 score compared to baseline.

Primary analysis of H3: We will compare the baseline and 6-month time point using a paired t-test for each of the measures (PDA, DDD, PEth, GGT and WHODAS 2.0).

For PDA, the unit of analysis is the proportion of days X_{ij} in a month that participant i is abstinent during month j . To do the paired t-test, we use the two paired proportions X_{i0} (0 refers to the baseline measure) and X_{i6} (6 refers to the 6-month measure). We can use a t-test on the difference $D_i = (X_{i6} - X_{i0})$. This should be a reasonable approximation because the averages X over roughly $n = 30$

days should be approximately Gaussian. The Gaussian approximation can be improved by using the variance stabilizing transformation

$$Y_{ij} = 2 \arcsin \sqrt{X_{ij}}$$

Thus, we will do a t-test using the differences $2[\arcsin \sqrt{X_{i6}} - \arcsin \sqrt{X_{i0}}]$. With $n = 3$ participants, we have little power unless the effect is large (e.g., if PDA moves from 0.05 to 0.50).

Secondary analysis of H3: To assess the course of PDA, DDD, PhEt, GGT, and WHODAS 2.0 over the duration of the study while taking into account the repeated measures (13 measures for each participant – one at baseline and 12 post-DBS), we will use a **mixed-effects model**:

$$Z_{ij} = \mu + \alpha_i + \tau_j + \epsilon_{ij}$$

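### The PDA limb of the alcohol-worsening boundary (Protocol 11.1 and 11.3) carries the wrong multiplier, so as written it sets no size of worsening; a halving of baseline PDA is probably meant but is not stated

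*Protocol*

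**What the plan says.** Protocol 11.3 gives the boundary as "Increased alcohol use in one participant compared to baseline (>2x baseline DDD or <2x PDA) that did not improve with adjusting DBS settings", identified at 3 consecutive follow-up visits. Section 11.1 uses the same limbs. The word baseline stands before DDD but not before PDA, and the limbs are joined by "or", so PDA alone in one participant is enough.

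The two sections attach different force to it. Section 11.1 says "The study will be discontinued (pending DSMB review) if any of the following occurs", and adds that with a justified mitigation plan "then the study could resume if the DSMB, IRB, and FDA agree". Section 11.3 is softer: "Circumstances that may warrant termination or suspension include, but are not limited to".

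Three other places bear on the reading:

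- **Direction of benefit.** H3 in 12.4 (Protocol and SAP): "Specifically, LP DBS increases PDA, and decreases DDD, PEth, GGT and WHODAS 2.0 score compared to baseline".
- **Measurement window.** Protocol 3.3 takes drinking "over the past 180 days for baseline evaluation, and over the past 30 days for follow-up evaluations after DBS implantation".
- **Participant-level step.** Under Protocol 9.1, increased use first leads to adjusted settings and a psychiatric evaluation. If use remains "elevated compared to baseline during two following evaluations, we will turn the DBS off and consult with the DSMB". No size of increase is given there.

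The SAP reproduces Section 12 only and does not restate the boundary.

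**The concern.** A worsening limit on a measure where higher is better should lie below the participant's baseline. This one lies at twice baseline, on the improvement side.

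The DDD limb asks for a doubling. That separates the study-level boundary from the step in 9.1, which acts on any persistent increase in one participant at about the same time (the evaluation that shows the increase plus two further evaluations, against 3 consecutive visits). The PDA limb as printed makes no such separation. A small persistent fall in abstinent days in one of three participants could then meet a criterion for discontinuing the study, and those applying it would have no stated number to check it against.

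**Working it through.** The documents give no error rate or other figure for this boundary, so there is nothing to reproduce. The main check is algebra.

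**Inputs.** Follow-up window of 30 days (3.3); PDA is a proportion between 0 and 1 (12.4); multiplier 2 (11.1, 11.3). The only starting PDA in the documents is 0.05, from the power remark in 12.4: "we have little power unless the effect is large (e.g., if PDA moves from 0.05 to 0.50". The other baselines below are assumptions.

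**Step 1: the possible readings.** Let b be baseline PDA and x be follow-up PDA.

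1. Exactly as printed, with no baseline: x < 2x, true for every x above 0.
2. Literal, with baseline supplied: x < 2b. No change (x = b) meets it whenever b > 0. So does a rise from 0.40 to 0.75, because 0.75 < 0.80. If b > 0.50, then 2b > 1 and full abstinence meets it.
3. Under the lead-in (use must have increased): x < b is required first, and x < b already implies x < 2b. The 2x adds nothing, and any fall qualifies.
4. Shorthand for a two-fold fall: x < 0.5b. This is a real threshold, but it is not what is printed.

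**Step 2: abstinent days of 30 that meet the limb** (whole k with k/30 < m × b):

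| Baseline b | Literal, m = 2 | Any fall, m = 1 | Halved, m = 0.5 |
|---|---|---|---|
| 0.05 | 0-2 | 0-1 | 0 |
| 0.10 | 0-5 | 0-2 | 0-1 |
| 0.30 | 0-17 | 0-8 | 0-4 |
| 0.60 | 0-30 | 0-17 | 0-8 |

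For example, at b = 0.30 the limits are k < 18, k < 9 and k < 4.5. At b = 0 no reading can be met.

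**Step 3: illustration of chance crossing.** Take a participant whose true PDA never changes, with k ~ Binomial(30, b), independent days and visits, and b known without error.

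- At b = 0.05, any fall means k ≤ 1: 0.95^30 + 30 × 0.05 × 0.95^29 = 0.2146 + 0.3389 = 0.5535. At 3 given visits: 0.5535³ = 0.170. Halved means k = 0: 0.2146³ = 0.0099.
- At b = 0.30, 3 given visits: any fall 0.4315³ = 0.080; halved 0.0302³ = 0.00003.
- For at least one run of 3 in 12 visits: any fall 69% at b = 0.05 and 44% at 0.30; halved 7.8% and below 0.1%. With days clustered within a window (assumed correlation 0.1): any fall 89% and 59%; halved 59% and 6.4%.

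**Step 4: how well the halved cut works.** If true PDA drops to a quarter of baseline, the halved limb is met at 3 given visits with probability 0.32 at b = 0.05, 0.57 at 0.10, 0.80 at 0.40 and 0.92 at 0.60. It works at moderate and high baselines and discriminates poorly at low ones.

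**The case against.** The strongest reply is that this is a notation slip any reader would repair. Paired with a doubling of DDD under a lead-in about increased use, the PDA limb is naturally taken as a two-fold fall. The lead-in already compares with baseline, so the missing second "baseline" matters little. That is probably the intent, and I accept that the missing word is secondary. But a halving is stated nowhere, and a safety limit should not have to be inferred.

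The second reply is that the boundary is not mechanical. It needs failure to improve after DBS adjustment, it is subject to DSMB review, and the study can resume. Section 9.1 acts on any persistent increase regardless. An over-sensitive limb errs toward caution. All of this stands and keeps the point small.

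A reader might go further and infer that the rule would stop the trial for a participant who is unchanged or improving. The documents do not support that: the lead-in restricts the criterion to increased use, and the DSMB reviews any crossing. Nor do the run probabilities in Step 3 give a false-stop rate. They describe an any-fall rule applied mechanically, without the DBS-adjustment condition or the DSMB's judgement, and they rest on assumed baselines, independent visits and an assumed correlation.

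**Conclusion.** The concern holds as a minor but real correction to a safety threshold. The sign is right and the multiplier is wrong: on the literal reading and on the lead-in reading alike, the PDA limb sets no size of worsening to match the DDD limb. This follows from the algebra alone and needs no distributional assumption. The day counts need only the 30-day window and a given baseline; the chance-crossing figures are illustrative.

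It does not follow that a worsening participant would be missed, since 9.1 acts on any persistent increase. No endpoint analysis depends on the rule.

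**What to change.** In both 11.1 and 11.3, replace `<2x PDA` with `<0.5x baseline PDA`.

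Add a note for the DSMB's pre-initiation meeting (13.5). At a baseline PDA of 0.05 only 0 of 30 abstinent days meets the halved cut, and at baseline 0 nothing can, so in that range the DDD limb and Section 9.1 must carry the protection. An absolute-change rule for low baselines is optional; the documents give no basis for a particular value.

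The cost is a short amendment in two places, with IRB approval (14.1), any notice required under the IDE (6.1) and notification of the DSMB. There is no cost in data or to participants.
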